8.4 Detection of Bias

This study has been designed to minimize potential bias by the use of randomization of subjects into treatment groups and the use of blinding. Other factors that may bias the results of the study include:

- Major protocol deviations likely to impact the analysis and interpretation of the efficacy endpoints
- Subject level unblinding before final database lock and formal unblinding

Important protocol deviations likely to impact the analysis and interpretation of the efficacy endpoints will be tabulated in the Clinical Study Report (CSR).

Any unblinding of individual subjects prior to formal unblinding of the study will be documented in the CSR. The impact of such unblinding on the results observed will be assessed.

Additional sensitivity analyses may be included to assess the impact of potential biases on the primary endpoint. If any sensitivity analyses are required to evaluate potential biases in the study's conclusions, then the sources of the potential biases and results of the sensitivity analyses will be documented in the CSR.

8.5 Outliers

Extreme data points will be identified during the blinded review of the data prior to database lock. Such data points will be reviewed with clinical data management to ensure accuracy. The primary analyses will include outliers in the data. Sensitivity analyses may be undertaken if extreme outliers for a variable are observed.

8.6 Distributional Characteristics

Distributional assumptions for the primary and secondary endpoints will be assessed. If the assumptions are not met, then alternative methods will be utilized. The use of alternative methods will be fully justified in the CSR.

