9.1.2 Multiplicity Adjustment

The primary and secondary efficacy endpoints will be hierarchically ranked for testing to control the overall type I error rate in claiming statistical significance at the two-sided 0.05 significance level. Specifically, for the primary efficacy endpoint (modified sPGA-G response at Week 16), if the two-sided p-value from the comparison between apremilast arm and placebo arm is below 0.05, the outcome will be considered statistically significant and apremilast will be declared effective. For any secondary endpoint, statistical significance will be claimed only if its two-sided p-value is below 0.05 and tests for the primary endpoint and all previous secondary endpoints are significant at the two-sided 0.05 level. The proposed test sequence for the primary and secondary efficacy endpoints is listed as the following:

- Proportion of subjects with modified sPGA-G score of clear (0) or almost clear (1) with at least a 2-point reduction from baseline at Week 16
- Proportion of subjects achieving an overall sPGA score of clear (0) or almost clear (1) with at least a 2-point reduction from baseline at Week 16
- Proportion of subjects with at least a 4-point improvement in GPI-NRS item score within the GPSS for subjects with a baseline score of ≥ 4 at Week 16
- Change from baseline in affected BSA at Week 16
- Change from baseline in DLQI total score at Week 16
- Change from baseline in GPSS total score and individual items scores at Week 16

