9.3 Important Protocol Deviations

Important Protocol Deviations (IPDs) categories are defined by the study team before the first subject's initial visit and updated during the IPD reviews throughout the study

prior to database lock. These definitions of IPD categories, subcategory codes, and descriptions will be used during the course of the study. Eligibility deviations are defined in the protocol.

Protocol deviations and important protocol deviations will be categorized by the Clinical Research Physician (CRP). A list of protocol deviations and important protocol deviations for all subjects for week 16 analysis will be defined prior to the Week 16 data restriction and unblinding (i.e., prior to the unblinding of double-blind placebo-controlled phase data). The list of protocol deviations and important protocol deviations for all subjects for final analysis will be finalized prior to the final database lock. This listing of important protocol deviations for week 16 analysis will also identify which subjects are to be excluded from the per-protocol population.

Protocol deviations and important protocol deviations by treatment group and overall will be provided for the placebo-controlled phase for the ITT analysis set, and for the Apremilast extension phase for subjects who receive at least one dose of IP during the phase. Summary tables showing the number and percent of subjects with at least one protocol deviation and important protocol deviations and by each category of protocol deviations and important protocol deviations will be provided. Listings of subjects with protocol deviations and important protocol deviations will also be provided.

Additionally, protocol deviations and important protocol deviations related to COVID-19 will be summarized.

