9.5.2.2 Continuous Variables

The continuous variables for secondary endpoints include the following:

- Change from baseline in affected BSA at Week 16
- Change from baseline in DLQI total score at Week 16
- Change from baseline in GPSS total score and individual items scores at Week 16

The continuous efficacy endpoints will be analyzed based on the ITT analysis set using a mixed-effect model for repeated measures (MMRM) as the primary method. The MMRM model will use the change from baseline as the response variable and include treatment group, visit time, treatment-by-time interaction, and stratification factor as fixed effects, and the baseline value as a covariate. An unstructured covariance matrix will be used to model the correlation among repeated measurements. The Kenward-Roger adjustment will be used with restricted maximum likelihood (REML) to make proper

statistical inference. Within-group least-squares (LS) means and the associated SEs and 2-sided 95% CIs, treatment difference in LS means and the associated SEs and 2-sided 95% CIs and 2-sided p-values will be derived from the MMRM model for Week 16 and other scheduled visits (Week 2, 4, 8, and 12, if applicable) in the model.

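### Does SAP Section 8.6 leave the test for BSA, DLQI and GPSS change open to choice after unblinding?

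*SAP*

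**What the plan says.** SAP Section 8.6 has three sentences and sits in Section 8, on data screening and acceptance. "Distributional assumptions for the primary and secondary endpoints will be assessed". Then: "If the assumptions are not met, then alternative methods will be utilized". Last: "The use of alternative methods will be fully justified in the CSR". It goes no further.

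SAP Section 9.5.2.2 analyses change in BSA, DLQI total and GPSS "using a mixed-effect model for repeated measures (MMRM) as the primary method", with unstructured covariance, REML and the Kenward-Roger adjustment.

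SAP Section 9.1.2 tests in a fixed order. A secondary claim needs its own two-sided p-value below 0.05 and requires that "tests for the primary endpoint and all previous secondary endpoints are significant at the two-sided 0.05 level". Ranks 1 to 3 are binary endpoints tested by CMH. Rank 4 is BSA change, rank 5 is DLQI change, and the last entry reads "Change from baseline in GPSS total score and individual items scores at Week 16".

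Two nearby rules are tighter. Section 8.5 identifies outliers in a blinded review before database lock and adds: "The primary analyses will include outliers in the data". Section 9.3 says that the list of deviations for the Week 16 analysis "will be defined prior to the Week 16 data restriction and unblinding".

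**The concern.** Section 8.6 is worded as an obligation, not an option, yet it does not define what sets it off. It has no diagnostic, no threshold, no substitute method, no date relative to the Week 16 unblinding and no blinding requirement. The justification is deferred to the CSR, which is written when results are known. It does not say whether the alternative supplies the p-value for the sequence or only supports the MMRM result.

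The exposed tests are the continuous ones: BSA (1) + DLQI total (1) + GPSS total (1) + GPSS items (8) = 11. BSA comes first among them, so its verdict decides whether the other ten may be tested. If the method at rank 4 could be chosen with the results in view, 0.05 would not be guaranteed at that step. Even without misuse, two analysts might use different tests and disagree on whether DLQI and GPSS are reached.

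**Working it through.** **1. The plan's own figure.** The only sizing figure is for the binary primary endpoint (SAP Section 3.2: 25% v 10%, two-sided 0.05, 85% power, 20% dropout). With pooled rate (0.25 + 0.10)/2 = 0.175:

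n per arm = [1.960·√(2·0.175·0.825) + 1.036·√(0.25·0.75 + 0.10·0.90)]² / 0.15² = (1.053 + 0.546)² / 0.0225 ≈ 113.7, so 114.

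114/0.8 = 142.5, so 143 per arm and 286 in all. Power at 143 × 0.8 = 114.4 evaluable per arm is 85.2%. The figure reproduces and does not depend on Section 8.6.

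**2. Which test the documents name for ranks 4 to 6.**

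- SAP Section 9.5.2.2: MMRM is the primary method, specified in full.
- SAP Section 8.3.1, Table 1: MMRM is the only entry for BSA, DLQI and GPSS change in Weeks 0–16. The table concerns missing data, so this is supporting evidence only.
- Protocol Section 9.6.1.2: MMRM is again primary. The second model, ANCOVA with LOCF, is a sensitivity analysis, and there is no distributional escape clause.
- SAP Section 10: the one listed change from the protocol is the removal of LOCF. Replacing MMRM is not listed.
- SAP Section 8.1: the aim of Section 8 is to screen the data against the needs of the planned analyses. That is a data check, not a review of results, although it does not itself require blinding.

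Nothing names a competing confirmatory test. The specific section governs; Section 8.6 is a generic conditional clause beside it.

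**3. Error rate at rank 4.** The documents give no BSA distribution, so three were assumed:

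- n = 228 (2 × 114), 1:1 within stratum.
- Baseline below 10%: 1 + 9·Beta(1.2, 1.5).
- Baseline 10% or more: 10 + U(0,10) in 40% of subjects (mild skew); 10 + Exp(mean 8) in 45% (moderate); 10 + Exp(mean 12) in 45% (strong).
- Week 16 BSA = baseline·exp(N(−0.2, SD) + effect), SD 0.25, 0.4 and 0.6.
- Single-visit ANCOVA (treatment, stratum, baseline) stands in for MMRM.
- 10,000 null trials per scenario, so the Monte Carlo SE near 5% is √(0.05·0.95/10,000) ≈ 0.2 points.

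| Null rejection | Mild | Moderate | Strong |
|---|---|---|---|
| Planned type (ANCOVA) | 5.2% | 4.8% | 5.1% |
| Rank ANCOVA | 5.1% | 4.8% | 5.0% |
| Preset switch (Shapiro p < 0.05 to rank ANCOVA) | 5.1% | 4.8% | 5.0% |
| Smaller p of two methods | 7.2% | 7.0% | 7.7% |
| Smallest p of three (adding van Elteren) | 8.9% | 8.6% | 9.2% |

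The switch row equals the rank row because the Shapiro check fired in every trial of a re-run of these scenarios. It therefore shows the result of always switching. With normal errors (n = 228, 4,000 null trials) the check fired in 5.0% of trials, the switched test rejected 4.5%, and the smaller p of two gave 5.6%. A case in which the check fires about half the time was not run.

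A separate null simulation on log-normal data, 114 to 143 per arm, gave 4.5–5.0% for any single fixed method and 7.3–7.5% for the smaller p of two.

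**4. What each choice costs.** Effects of −0.10 and −0.20 on the log scale mean Week 16 BSA lower by 1 − e^(−0.10) ≈ 10% and 1 − e^(−0.20) ≈ 18%. With 3,000 trials per effect size:

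| | Mild | Moderate | Strong |
|---|---|---|---|
| Verdicts differ, 10% lower | 11.6% | 17.3% | 13.0% |
| Verdicts differ, 18% lower | 0.1% | 12.1% | 24.5% |
| Power, 18% lower: planned type | 99.8% | 82.0% | 42.3% |
| Power, 18% lower: rank ANCOVA | 100% | 91.0% | 58.2% |

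**5. Ranks 1 to 3.** Taking the better of CMH and chi-square gave 4.7–5.1% under the null (20,000 trials per setting, response 10% to 25%). Section 8.6 has almost nothing to act on there.

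**The case for a change.** The strongest case for a change is that the text, taken alone, displaces MMRM once someone declares a failed assumption, and nobody can say in advance what counts as failure. Signing the SAP before unblinding fixes the words, not a later switch that the words allow. Sections 8.5 and 9.3 show that the sponsor can write such rules with blinding and timing. The planned test already holds its level under skew, so the clause is not needed for validity. One sentence giving Section 9.5 precedence would close the matter.

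Part of this stands. The four omissions are real, no other section supplies them, and the order of precedence is inferred from several places instead of being stated. If BSA is skewed, the planned and rank tests can disagree often enough to matter.

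The rest does not carry a change. Section 8.6 is triggered by failed assumptions, not by the smaller p-value. The inflated rates describe selection after unblinding, which the SAP does not describe and which would contradict Section 9.5.2.2. Nor is locking MMRM free: under the assumed strong skew it gives 42% power at rank 4 against 58% for the rank test. Naming the rank test instead would give up the difference in LS means that Section 9.5.2.2 reports. Either choice is defensible, so this is a trade-off for the sponsor, not an error to correct.

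**Conclusion.** No change follows. Section 8.6 is a loosely written general clause, but the plan names one confirmatory method for BSA, DLQI and GPSS change, in both documents, and records no departure from it. An analyst would take MMRM into the Section 9.1.2 sequence and report any alternative beside it.

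In the cases simulated, a switch made on an assumption check alone stayed at 4.5–5.1%. The 7.0–9.2% figures are upper bounds under skew. They need selection with results in view, success at ranks 1 to 3 and a true BSA null.

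All the simulated rates rest on assumed BSA distributions and on single-visit ANCOVA in place of MMRM. DLQI and GPSS were not simulated. The argument from the documents does not depend on them. What is left is an unstated precedence rule that could matter only at ranks 4 to 6.

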8.7 Validation of Statistical Analyses

Programs will be developed and maintained, and output will be verified in accordance with current risk-based quality control procedures.

Tables, figures, and listings will be produced with validated standard macro programs where standard macros can produce the specified outputs.

The production environment for statistical analyses consists of Amgen-supported versions of statistical analysis software; for example, the SAS System version 9.4 or later.

9. Statistical Methods of Analysis

9.1 General Considerations

9.1.1 General Approaches to Efficacy Analysis

The intent-to-treat principle will be used in statistical analyses for efficacy endpoints. For the Placebo-controlled Phase (Weeks 0-16), efficacy evaluations will be conducted using the intent-to-treat (ITT) analysis set defined as all randomized subjects. Statistical comparisons will be made between the two treatment arms (placebo or apremilast). For the Apremilast Extension Phase (Weeks 16-32), efficacy evaluations will be conducted using subjects who entered the phase from both treatment arms.

Descriptive statistics (n, mean, SD, SE, median, Q1, Q3, min, max) will be presented for appropriate endpoints at specified time points. Specifically, for continuous variables, descriptive statistics for assessment values and change (plus percentage change when specified) from baseline will be provided. Binary variables will be summarized with frequency tabulations; shift tables will be provided when appropriate.

Statistical comparisons will be made between placebo arm and apremilast arm; the null hypothesis is that the effects of the two treatment arms (i.e., placebo vs. apremilast) have no difference. Statistical tests will be at the two-sided 0.05 significance level and the corresponding p-values and two-sided 95% confidence intervals will be reported.

Baseline definition for all efficacy endpoints is given in [Section 5.4](#). Change from baseline is calculated as post-baseline visit value minus the baseline value. Percent change from baseline is defined as $100^* \text{ Change from baseline/Baseline value (\%)}$. Handling of time points is described in [Section 5.5](#).

In the event that any site errors are made in specifying the stratification factor (baseline BSA <10% or BSA \geq 10%) for randomization, the classification of the stratification factor in all efficacy analyses will be based on the actual classification according to the clinical database.

In the data as observed (DAO) analyses, only subjects with sufficient data at the time point under consideration will be included.

9.1.2 Multiplicity Adjustment

The primary and secondary efficacy endpoints will be hierarchically ranked for testing to control the overall type I error rate in claiming statistical significance at the two-sided 0.05 significance level. Specifically, for the primary efficacy endpoint (modified sPGA-G response at Week 16), if the two-sided p-value from the comparison between apremilast arm and placebo arm is below 0.05, the outcome will be considered statistically significant and apremilast will be declared effective. For any secondary endpoint, statistical significance will be claimed only if its two-sided p-value is below 0.05 and tests for the primary endpoint and all previous secondary endpoints are significant at the two-sided 0.05 level. The proposed test sequence for the primary and secondary efficacy endpoints is listed as the following:

- Proportion of subjects with modified sPGA-G score of clear (0) or almost clear (1) with at least a 2-point reduction from baseline at Week 16
- Proportion of subjects achieving an overall sPGA score of clear (0) or almost clear (1) with at least a 2-point reduction from baseline at Week 16
- Proportion of subjects with at least a 4-point improvement in GPI-NRS item score within the GPSS for subjects with a baseline score of ≥ 4 at Week 16
- Change from baseline in affected BSA at Week 16
- Change from baseline in DLQI total score at Week 16
- Change from baseline in GPSS total score and individual items scores at Week 16

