Other secondary endpoints of response will include the proportion of subjects with a 4-point reduction (improvement) from baseline in the Genital Psoriasis Itch Numeric Rating Scale (GPI-NRS) score at Week 16. The GPI-NRS is one of eight components of the validated Genital Psoriasis Symptoms Scale (GPSS) which was developed to assess symptoms that are particularly burdensome to subjects with genital psoriasis (Gottlieb, 2018). The GPSS was modeled after the Whole Body Itch numeric rating scale (NRS) instrument, which has been previously validated in subjects with moderate to severe plaque psoriasis (Naegeli, 2015). While all eight components of the GPSS and total symptoms score will be included as a secondary endpoint, the significant impact of itch on quality of life in subjects with genital psoriasis warrants additional attention. Pruritus is a common and frequently reported symptom of plaque psoriasis, occurring on a daily basis in 77% of subjects with extensive psoriasis (Yosipovitch, 2000). In an observational, multicenter study of 354 subjects with current and/or previous genital psoriasis, itch was reported by 86% of participants (Ryan, 2015). In study PSOR-025, assessment of genital itch will be conducted from baseline (Visit 2) through the Apremilast Extension Phase. In addition to GPI-NRS, change from baseline in affected BSA, change from baseline in Dermatology Life Quality Index (DLQI) total score, and change from baseline in GPSS total score and individual items scores will be assessed at Week 16.

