5.1.3 Genital Psoriasis Symptoms Scale (GPSS)

The GPSS is a patient-administered assessment of eight symptoms: itch, pain, discomfort, stinging, burning, redness, scaling, and cracking. Respondents are asked to answer the questions based on their psoriasis symptoms in the genital area. Numeric

rating scales (NRS) are used to assess the self-reported overall severity of each of the eight symptoms individually in the genital area on an 11-point horizontal scale anchored at 0 (no) and 10 (worst imaginable). The overall severity for each individual symptom from patient's genital psoriasis is indicated by selecting the number from 0 to 10 that best describes the worst level of each symptom in the genital area in the past 24 hours. Each of the eight individual items will receive a score of 0 to 10 and will be reported as item scores for itch, pain, discomfort, stinging, burning, redness, scaling, and cracking.

In addition, a total score ranging from 0 (no genital psoriasis symptoms) to 80 (worst imaginable genital psoriasis symptoms) will be reported.

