5.1.4 Genital Psoriasis Itch Numeric Rating Scale (GPI-NRS)

The GPI-NRS is one of eight components of the validated GPSS which was developed to assess symptoms that are particularly burdensome to subjects with genital psoriasis. Patient self-reported severity score of itch in the genital area on an 11-point horizontal scale anchored at 0 (no) and 10 (worst imaginable) will be reported.

For a post baseline visit, the GPI-NRS response is defined as ≥ 4 points reduction (improvement) from baseline in the GPI-NRS score for subjects with baseline score of ≥ 4 . Change from baseline in the GPI-NRS score will also be derived.

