8.3 Handling of Missing and Incomplete Data

8.3.1 Efficacy endpoints

Missing data handling methods applied to the analysis for each efficacy endpoints is summarized as below:

Table 1. Summary of missing data handling method applied to the analysis for each efficacy endpoint

Analysis Set [a]	Week	Endpoint	Imputation Method [b]
ITT, PP	0-16	Modified sPGA-G response	MI, NRI, DAO
ITT	0-16	sPGA response	MI, NRI, DAO
ITT	0-16	GPI-NRS response	MI, NRI, DAO
ITT	0-16	BSA change and percent change from baseline	MMRM
ITT	0-16	DLQI change from baseline	MMRM
ITT	0-16	GPSS total score change from baseline	MMRM
ITT	0-16	GPSS individual items scores change from baseline	MMRM
ITT	0-16	DLQI-Q#9 change from baseline	MMRM
ITT (Subjects entered extension phase)	16-32	sPGA-G response, sPGA response, GPI-NRS response	NRI, DAO
ITT (Subjects entered extension phase)	16-32	BSA change and percent change from baseline, DLQI change from baseline, GPSS total score change from baseline, GPSS individual items scores change from baseline, GPI-NRS change from baseline, DLQI-Q#9 change from baseline	DAO

Note: MI = Multiple Imputation; NRI = Non-responder imputation; DAO = Data as Observed; MMRM= Mixed-effect model for repeated measures

[a] See [Section 6](#)
[b] See [Section 9.5](#)

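### The last rank of the testing hierarchy holds nine GPSS hypotheses with no rule among them, so the claimed 5% error control is not delivered at that rank

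*SAP*

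**What the plan says.** SAP 9.1.2 says of the endpoints in its confirmatory list that they "will be hierarchically ranked for testing to control the overall type I error rate in claiming statistical significance"; the level is 0.05, two-sided. Protocol 9.6.1.3 makes the same claim with the same list. For a secondary endpoint, "statistical significance will be claimed only if its two-sided p-value is below 0.05" and every earlier test in the list is significant too.

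The six ranks are:

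1. modified sPGA-G response (primary)
2. sPGA response
3. GPI-NRS response
4. change in BSA
5. change in DLQI total
6. "Change from baseline in GPSS total score and individual items scores at Week 16"

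SAP 5.1.3 says of the GPSS: "Each of the eight individual items will receive a score of 0 to 10". It also defines a total running from 0 to 80. SAP 8.3.1, Table 1, lists the total in one row and "GPSS individual items scores change from baseline" in another, each analysed by MMRM. SAP 9.5.2.2 says for the continuous secondary endpoints that "treatment difference in LS means and the associated SEs and 2-sided 95% CIs and 2-sided p-values will be derived from the MMRM model". SAP Section 10 lists one departure from the protocol, the removal of LOCF, and nothing on multiplicity.

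**The concern.** A fixed sequence controls the familywise error because each step is a single test at full alpha, and testing stops at the first failure. Ranks 1 to 5 meet that condition. Rank 6 does not: it is one line in the list but nine null hypotheses, each with its own model and p-value. Nothing says which is tested first, whether the total must succeed before the items are looked at, whether alpha is shared, or whether all nine must succeed together.

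At stake are claims about single symptoms. If the trial does well and reaches rank 6, a difference in pain, burning or cracking could be reported as significant under a procedure said to hold 5%, when the real chance of a false claim is higher. Genital symptoms are a stated secondary objective, so such claims are likely to be used.

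**Working it through.** **Count of hypotheses.** Eight items plus one total: 8 + 1 = 9.

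**The plan's 5%, ranks 1 to 5.** Take the first true null hypothesis among these ranks. No false claim can occur at or after it unless its own test rejects, which has probability at most 0.05. The stated control therefore holds for ranks 1 to 5. If the drug does nothing at all, the primary test alone caps the error at 5%. The problem arises only when the effects at ranks 1 to 5 are real and some GPSS hypotheses are null.

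**Error at rank 6 under the stated rule.** Inputs:

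- Level: two-sided 0.05, so c = 1.96 (SAP 9.1.2).
- Number of null items, k: 7, 4 or 2 (assumed). k = 7 means that itch improves, and with it the total, while the other items do not. Itch is a natural item to treat as improved, because rank 3 is its responder version: "The GPI-NRS is one of eight components of the validated GPSS" (SAP 5.1.4).
- Correlation ρ between the item test statistics: not in the documents. Assumed equal for all pairs, at 0.5, 0.8 and 0.9.

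Write each null statistic as Z_j = √ρ·U + √(1−ρ)·E_j, with U and E_j independent standard normal. Then

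P(at least one |Z_j| > c) = 1 − ∫ φ(u)·[Φ((c − √ρ·u)/√(1−ρ)) − Φ((−c − √ρ·u)/√(1−ρ))]^k du.

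The limits are a useful check. At ρ = 1 the answer is 0.05; at ρ = 0 with k = 7 it is 1 − 0.95^7 = 0.302. Between them:

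| Null items k | ρ = 0.5 | ρ = 0.8 | ρ = 0.9 |
|---|---|---|---|
| 7 | 23% | 15% | 11% |
| 4 | 16% | 11% | 9% |
| 2 | 9% | 8% | 7% |

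If all nine GPSS hypotheses are null while ranks 1 to 5 succeed, simulation with the total as the standardised sum of the items gives 25%, 16% and 12%.

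**Allowing for the chance of reaching rank 6.** The table is conditional on ranks 1 to 5 all passing. Treating that event as independent of the null item statistics, multiply by its probability. At an assumed 0.70, the k = 7 row becomes 0.70 × 0.23 = 16%, 0.70 × 0.149 = 10% and 0.70 × 0.114 = 8%. It falls below 5% only if the chance of reaching rank 6 is under about 0.05/0.23 = 22%, 0.05/0.149 = 34% or 0.05/0.114 = 44%. In the mildest case shown (k = 2, ρ = 0.9) it is 0.70 × 0.07 = 4.9%.

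**Error under a controlled rule.** Test the total first and then the eight items with Holm. The worst case is that every truly improved item has already been rejected, so the k null items face a first threshold of 0.05/k. For k = 7 the same formula at level 0.05/7 gives about 4%, 3% and 2%; for k = 4 at level 0.05/4 it gives about 4%, 3% and 3%. All are below 5%.

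**The case against.** **The text may be silent rather than permissive.** The claim rule is written per endpoint, and protocol 1.3.2 treats the GPSS as one: "While all eight components of the GPSS and total symptoms score will be included as a secondary endpoint". On that view rank 6 is a single endpoint and nobody has licensed nine separate claims. Two readings would keep control: all nine must be significant, or the nine are tested in the order the symptoms are listed. It is true that the text does not expressly allow separate claims. But the rule needs one p-value, none is defined for the bundle, and the planned models produce nine. Neither protective reading is written down, so the choice could be made after the results are known.

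**The seven-null case is near the upper end.** This stands. Redness and scaling are among the seven, and protocol 6.4 makes erythema the dominant feature of the primary endpoint, with scaling also graded. A real primary effect with no effect on patient-rated redness or scaling is unlikely. An itch-only effect would also move the total little. With equal item variances, an itch mean z of 3 to 5 gives the total a mean z of 3/√(8 + 56 × 0.9) = 0.4 at the low end and 5/√(8 + 56 × 0.5) = 0.8 at the high end. The rows for two to four null items, 7% to 16%, are the more plausible range.

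**Only claims favouring apremilast matter.** Those are half of the two-sided figures: about 11.5%, 7.4% and 5.7% for seven nulls and 4.5%, 3.9% and 3.5% for two, against a nominal 2.5%. The inflation remains but is modest when few items are null or correlation is high.

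**Independence of rank 6 from ranks 1 to 5 is doubtful.** Rank 3 is a GPSS item, and DLQI item 1 covers itch, soreness, pain and stinging. The unconditional and break-even figures are therefore rough, and could err in either direction. Strong control, however, must hold for every pattern of effects. When the effects at ranks 1 to 5 are large, rank 6 is almost always reached and the conditional figures apply.

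**Conclusion.** The concern holds. The plan states 5% familywise control, and the rule it gives does not deliver this at rank 6. Applied to each of the nine hypotheses, the rule gives a conditional false-claim rate of about 7% to 16% with two to four null items and 11% to 23% with seven, for correlations of 0.5 to 0.9. The correlations, the number of null items and the chance of reaching rank 6 are all assumptions. The existence of the gap does not depend on them; only its size does.

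The reach is limited. Nothing follows rank 6, so no error passes on. The primary conclusion, the 286-subject sample size and the claims at ranks 1 to 5 are untouched. It should be fixed because it concerns a stated property of the confirmatory procedure, but it does not threaten the trial's main result.

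**What to change.** Before Week 16 unblinding, which is also when SAP Section 1 requires the SAP to be final, replace the last line of SAP 9.1.2 with rank 6: change from baseline in GPSS total score at Week 16. Then take one of two routes:

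- **(a)** Add rank 7: change from baseline in the eight GPSS item scores at Week 16, tested only if rank 6 is significant, with Holm adjustment at two-sided 0.05.
- **(b)** Remove the items from the hierarchy and report their p-values as nominal.

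Another written rule that controls the error, such as a stated fixed order of the items, would serve equally well. Gating on the total and then testing all items unadjusted would not: with the total truly improved and seven items null, the false-claim rate is still the 23%, 15% and 11% in the table.

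Make the matching edit to protocol 9.6.1.3, or record the change in SAP Section 10. The cost is a few lines of text, with no patients and no new data. Route (a) gives up some item-level claims, chiefly when the effect is confined to one or two symptoms and the total does not reach significance. Itch keeps its own test at rank 3. Route (b) gives up confirmatory item claims altogether.
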